### 2.2 SECONDARY OBJECTIVES

1. To evaluate the efficacy of LAI (590 mg) administered QD when added to a multi-drug regimen on the six minute walk test (6MWT) at Month 6 compared to a multi-drug regimen alone
2. To evaluate the efficacy of LAI (590 mg) QD when added to a multi-drug regimen on the durability of treatment success 3 months after the end of total treatment course (negative sputum culture after 3 months off treatment)
3. To evaluate the efficacy of LAI (590 mg) administered QD when added to a multi-drug regimen for time to culture conversion compared to a multi-drug regimen alone
4. To evaluate the efficacy of LAI (590 mg) administered QD, when added to a multi-drug regimen, for achieving sustainability (consecutive negative sputum cultures [with no more than 2 consecutive monthly broth positive cultures] for 12 months on treatment) compared to a multi-drug regimen alone
5. To evaluate the efficacy of LAI (590 mg) administered QD when added to a multi-drug regimen on the 6MWT at EOT compared to a multi-drug regimen alone
6. To evaluate patient reported symptoms of NTM and change from Baseline (Day 1) in quality of life scores on the St. George's Respiratory Questionnaire (SGRQ) at Month 6.

Protocol Amendment #3 version: 22 February 2016

*This protocol is solely for the purpose of communicating information about the investigational drug between Insmid Incorporated and study personnel. Information is not to be reproduced, abstracted or used for sharing of information for any other purpose, whatsoever, except with the written permission of Insmid Incorporated.*

Confidential

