## 3 INVESTIGATIONAL PLAN

### 3.1 STUDY DESIGN

The Screening window allows time for sputum culture results, susceptibility by minimum inhibitory concentration (MIC) determination, and scheduling of Screening assessments. Any delay in obtaining microbiological results and MICs must be reported to the Sponsor immediately and documented within the study source documents. In the event that sputum culture results are not known by 8 weeks (Day -14), the Baseline (Day 1) visit should be scheduled as soon as possible in order to maintain the Screening window, and an extension of the Screening window to 14 weeks is allowed, if necessary. If sputum culture results are known prior to 8 weeks (Day -14), the Screening window of 10 weeks must be maintained. Once Screening assessments are complete and sputum culture results are known, eligible

Protocol Amendment #3 version: 22 February 2016

*This protocol is solely for the purpose of communicating information about the investigational drug between Insmid Incorporated and study personnel. Information is not to be reproduced, abstracted or used for sharing of information for any other purpose, whatsoever, except with the written permission of Insmid Incorporated.*

Confidential

subjects will be randomized 2:1 to LAI administered QD plus a multi-drug regimen or a multi-drug regimen alone. The primary endpoint will assess culture conversion by Month 6.

Sputum culture results will only be available to the site after the Month 6 sputum result is known, in time for the Month 8 visit. At Month 8 (-28 to +7 days), after all sputum culture results are known, up to and including Month 6, subjects will be assessed as converters or non-converters.

All converters will remain in Study INS-212 (Section 4.6). All converters who, after culture conversion, subsequently have MAC-positive sputum cultures in liquid broth media (agar negative) for 1 or 2 consecutive months only, will also remain in Study INS-212. These subjects will continue on their randomized treatment regimen until they complete a total of 12 months of treatment (EOT), starting from the first of 3 negative cultures that defines culture conversion. These subjects will return after the EOT visit for 28 day, 3, 6 and 12 months off-treatment follow-up visits. The 12 months off-treatment follow-up visit will be the end of study (EOS) visit. No NTM treatment will be administered during the off-treatment phase.

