#### **4.6 DEFINITIONS OF CONVERTER AND COMPLETER**

A converter is defined as a subject who has 3 consecutive monthly MAC-negative sputum cultures at any time within the first 6 months of the study.

Relapse or recurrence is defined as having MAC-positive sputum cultures in liquid broth media (agar negative) for 3 or more consecutive months, or having 1 MAC-positive sputum culture on solid media (agar positive) after achieving culture conversion.

A non-converter is defined as a subject who does not have 3 consecutive monthly MAC-negative sputum cultures at any time within the first 6 months of the study.

A completer for this study will be defined as follows:

1. A converter who successfully completes 12 months on the same treatment regimen beginning from the first of 3 negative cultures that defined conversion and successfully completes the 12 months off-treatment EOS follow-up visit.
2. A non-converter who successfully completes all dosing and protocol requirements up to and including the Month 6 study visit.

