## 7 STUDY VARIABLES AND METHODS OF ASSESSMENT

### 7.1 PRIMARY ENDPOINT VARIABLES

#### 7.1.1 Sputum Collection, Transport, and Assessment

Pre-dose expectorated or induced sputum specimens (approximately 3 mL) are required at Screening, Day 1, at Months 1 through 6, at Months 8 and 12, at EOT, at the 28 day, the 3, 6, and 12 months off-treatment visits. To improve the probability of obtaining a good sputum specimen, at least 2 and preferably 3 sputum samples will be obtained from each subject at each

Protocol Amendment #3 version: 22 February 2016

*This protocol is solely for the purpose of communicating information about the investigational drug between Insmid Incorporated and study personnel. Information is not to be reproduced, abstracted or used for sharing of information for any other purpose, whatsoever, except with the written permission of Insmid Incorporated.*

assessment. If a subject is unable to produce sputum spontaneously, one induced sputum specimen at the site will be acceptable. With the exception of the Screening samples (collected during the week following the Screening visit), each sputum sample will be collected on consecutive days prior to a scheduled visit. Subjects will refrain from administering LAI on the days sputum is obtained, starting 2 days prior to the scheduled visit, even if a spontaneous sputum cannot be obtained by the subject at home. At the scheduled visit, once sputum is collected (spontaneously or by induction), the administration of LAI can recommence. Sites are encouraged to notify subjects by telephone of this procedure 3 days prior to their scheduled visit. If a subject is unable to produce sputum independently, sputum may be induced as described in [APPENDIX 1](#), if these suggestions are safe for the subject. If a subject is still unable to produce sputum despite reasonable efforts, and they have already met the definition of converter, this will be recorded as a negative culture result at that time point.

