## 14 APPENDICES

### APPENDIX 1 SPUTUM INDUCTION SUGGESTIONS

#### **Introduction**

Collection of good sputum samples is critical to the success of this study. Sputum samples will be collected at the clinical site and also by the subject at home. To facilitate obtaining good sputum samples during the study visits at the clinic, sputum induction must be performed if the subject is unable to expectorate approximately 3.0 ml of sputum.

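### After conversion, a visit with no sputum is recorded as a negative culture, so durability and sustainability can be met without a further culture, on an effort standard the protocol states inconsistently

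*Protocol*

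**What the plan says.** Section 7.1.1 sets the rule. Its condition is "If a subject is still unable to produce sputum despite reasonable efforts, and they have already met the definition of converter", and its consequence is "this will be recorded as a negative culture result at that time point". It names no visits, and the same section schedules sputum "at Months 1 through 6, at Months 8 and 12, at EOT, at the 28 day, the 3, 6, and 12 months off-treatment visits". The rule is therefore open at every scheduled visit once a subject has converted.

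Section 2.2 describes durability as "negative sputum culture after 3 months off treatment", and sustainability as a run of negative cultures over 12 months on treatment, with limited tolerance for broth positives. For these two endpoints Section 9.6.2 counts relapse, rescue medication and death as failures. Lack of a specimen is not on that list. For the primary endpoint, Section 9.6.1 goes the other way: missing cultures that prevent evaluation make the subject a non-converter.

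On effort, Section 7.1.1 says "sputum may be induced as described in" Appendix 1, if this is safe for the subject. The introduction to Appendix 1 says of clinic visits that "sputum induction must be performed if the subject is unable to expectorate approximately 3.0 ml of sputum". Treatment is open label (Sections 5.6 and 9.3). On disclosure, Section 3.1 says "Sputum culture results will only be available to the site after the Month 6 sputum result is known", in time for the Month 8 visit.

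**The concern.** Both secondary endpoints are described in terms of negative cultures, yet after conversion an absent specimen enters the data as one. A single no-sputum visit can decide durability, which turns on the culture 3 months off treatment. The protocol asks for no flag to tell the two kinds of negative apart.

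The rule can only add successes, and only among converters. The plan expects four times the conversion rate on LAI, so most of any added successes should fall there.

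Reasonable efforts is not defined, and the two passages on induction disagree. The effort is made by staff who, from Month 8, know the arm and know that the subject is a converter. Section 7.2.1.2 requires a blinded assessor for the walk test, but nothing comparable protects sputum collection. At stake is how much of the between-arm difference in endpoints 2 and 4 rests on cultures and how much on missing specimens.

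**Working it through.** **Inputs (Section 9.1).** Conversion rates c are 20% on LAI and 5% on control. Durable conversion is 16% and 4%. Arm sizes are 174 and 87. The test is Fisher's exact, two-sided 0.05, with stated power of at least 83%. Durability among converters follows as d = 16/20 = 4/5 = 0.80 in each arm. The share u of converters with no sputum at the 3-month off-treatment visit is not in the protocol. I take it as 0.1 to 0.3, equal in both arms, and assume that converters without sputum are as durable as the rest.

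**The plan's own figure.** Exact enumeration at 16% vs 4% gives 83.2% power with the two-sided p taken as twice the one-sided p, and 85.7% with the minimum-likelihood p. Both agree with the stated figure.

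**Formulas, per arm.**
- True durable rate: c·d
- Rate as recorded under Section 7.1.1: c·[(1−u)·d + u]
- Rate if a real culture is required: c·(1−u)·d
- Successes without a culture: c·u, which is 20u points on LAI and 5u on control
- False excess (no sputum, but would have been positive): c·u·(1−d)

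The false excess in the between-arm difference is (20−5)·u·(1−d) points. At d = 0.80 this is 3u.

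**Results at d = 0.80** (true difference 12.0 points; power shown as doubled p / minimum-likelihood p).

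| u | As recorded | Difference | False excess | Power | Culture required | Difference | Power |
|---|---|---|---|---|---|---|---|
| 0.1 | 16.4% vs 4.1% | 12.3 | 0.3 | 84.4 / 86.8% | 14.4% vs 3.6% | 10.8 | 77.7 / 80.6% |
| 0.2 | 16.8% vs 4.2% | 12.6 | 0.6 | 85.6 / 87.8% | 12.8% vs 3.2% | 9.6 | 70.9 / 73.9% |
| 0.3 | 17.2% vs 4.3% | 12.9 | 0.9 | 86.6 / 88.7% | 11.2% vs 2.8% | 8.4 | 62.6 / 65.8% |

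**In subjects.** Expected converters are 0.20 × 174 = 34.8 and 0.05 × 87 = 4.35. At u = 0.2, about 7.0 LAI and 0.9 control subjects would count as durable with no 3-month culture. Of these, about 1.4 and 0.2 would be false successes (the same counts times 1−d = 0.2).

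**More relapse.** At d = 0.50 the false excess is 15·u·0.5 = 7.5u points. At u = 0.3 that is 2.25 points, so the difference rises from 7.5 to 9.75.

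**Extreme null case.** Suppose true durable rates were equal at 4%, that is d = 0.2 on LAI (0.20 × 0.2) and d = 0.8 on control (0.05 × 0.8). At u = 0.2 the recorded rates are 0.20 × (0.8 × 0.2 + 0.2) = 7.2% and 0.05 × (0.8 × 0.8 + 0.2) = 4.2%. Fisher rejection (minimum-likelihood p) rises from 3.3% at u = 0 to 10.6% at u = 0.2 and 20.4% at u = 0.3.

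Section 9.1 gives no planning rate for sustainability, so endpoint 4 cannot be sized in the same way.

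**The case against.** The best defence is that the rule is pre-specified, applies to both arms alike, and is clinically sensible: a patient who has improved may truly have no sputum. Several features should keep u low. Entry requires about 3 mL of sputum or willingness to be induced, each assessment seeks two to three samples, and induction is the back-up. Appendix 1 is titled as suggestions, so its one obligatory sentence may be a leftover. The statistical analysis plan was not available and may already contain a supportive analysis. All of this stands. It is why the convention can stay for the main analysis. It does not settle the effort standard, which sites take from the protocol.

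Four stronger readings are tempting but not supported:
- *The endpoints can be met with no culture at all.* The rule starts only after conversion, which needs three consecutive monthly negative cultures (Section 4.6). A relapse already shown by culture remains a failure.
- *The whole 20u vs 5u points is bias.* That counts every unconfirmed negative as false. Only the fraction 1−d is.
- *The rule costs power.* As recorded, power rises slightly. The lower figures are what a strict analysis would show.
- *Unblinded sites favour LAI.* Nothing in the protocol shows less effort in one arm. Everyone who continues after Month 8 is a converter, so converter status does not separate the arms. The LAI sputum PK subset (Section 7.4.1) also needs specimens at 28 days and 3 months off treatment, a reason to try harder on LAI.

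**Conclusion.** The point holds in a limited form. After conversion, endpoints 2 and 4 can be met without a further culture, on an effort standard that is undefined and stated inconsistently, in an open-label trial. The primary endpoint is not inflated.

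At the protocol's planning values the distortion of the durability difference is small: 0.3 to 0.9 points on 12.0 for u between 0.1 and 0.3. It grows if relapse is common or sputum is often absent, and it reaches the type I error only in an extreme scenario. These sizes assume equal u in both arms and the same durability with and without sputum. If converters without sputum are more often truly clear, the false excess is smaller. At equal u, the gain is larger on LAI unless the true loss of durability among control converters is at least four times that on LAI.

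The issue is mainly transparency: as the protocol stands, a reader could not tell how many successes were cultured.

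**What to change.** Keep the Section 7.1.1 convention for the main analysis and make four additions:

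1. Reconcile the induction wording in Section 7.1.1 with that in Appendix 1.
2. Apply the no-sputum rule only when an attempted induction, or the reason it was unsafe, is documented for that visit.
3. Flag no-sputum negatives separately from cultured negatives, and report them by arm and visit.
4. In Section 9.6.2, add one supportive Cochran-Mantel-Haenszel analysis of endpoints 2 and 4 in which a no-sputum visit does not count as negative, unless the statistical analysis plan already has one. Present it as the cautious bound, since some of these patients will truly be clear.

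The cost is one table and one documentation line. The supportive rates will be lower: at u = 0.2, for example, 12.8% vs 3.2% for durability, with Fisher power of about 71 to 74%. A non-significant supportive result should therefore not be read as overturning the main one.

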### **7.1.2 Microbiological Assessment**

Sputum specimens will be cultured in liquid media in addition to solid media (agar). If results are negative on agar, the liquid media will be held for 6 weeks before reporting as culture negative.

Standard antibiotic sensitivity testing using MICs will be routinely performed on bacterial isolates (Clinical and Laboratory Standards Institute [CLSI] M48-A and NCCLS M24-A)

Protocol Amendment #3 version: 22 February 2016

*This protocol is solely for the purpose of communicating information about the investigational drug between Insmmed Incorporated and study personnel. Information is not to be reproduced, abstracted or used for sharing of information for any other purpose, whatsoever, except with the written permission of Insmmed Incorporated.*

(Forbes 2008). All mycobacterial isolates will be banked for subsequent determination of amikacin susceptibility and selective molecular typing (Prammananan, et al. 1998).

Isolates of MAC will be identified to complex, using a commercial RNA probe (AccuProbe, Gen Probe, Inc.) and subsequently identified to species (*M. avium*, *M. intracellulare*, MAC “X” group) using molecular methodology (Cousins, et al. 1996).

## **7.2 SECONDARY ENDPOINT VARIABLES**

### **7.2.1 Six-minute Walk Test**

#### **7.2.1.1 Methodology**

A 6MWT of exertional capability will be performed at Baseline (Day 1) and at Months 4, 6, 8 and at EOT and 3 months off-treatment according to ATS guidelines (<http://ajrccm.atsjournals.org/cgi/content/full/166/1/111>). Overall fatigue and dyspnea (Borg scale) will be measured before and after subjects walk a prescribed course as far as they can in 6 minutes.

#### **7.2.1.2 Assessment**

The 6MWT must be conducted by a site member who is blinded to the subject’s open-label treatment assignment. The maximum distance achieved will be recorded in the eCRF.

### **7.2.2 Physical Examination**

#### **7.2.2.1 Methodology**

A physical examination of the head (external), eyes, ears, nose and throat, lungs, cardiovascular system, abdomen, musculoskeletal system, skin, lymph nodes, central nervous system, and, as appropriate, other body systems will be performed before the administration of study drug at every scheduled visit except at Months 1, 3, 5, 10, 14, at 28 days and 6 months off-treatment. The physical examination will also include weight; the measurement of height, without shoes, will only be done at Screening. All significant findings must be recorded in the eCRF as described below.

Protocol Amendment #3 version: 22 February 2016

*This protocol is solely for the purpose of communicating information about the investigational drug between Insmmed Incorporated and study personnel. Information is not to be reproduced, abstracted or used for sharing of information for any other purpose, whatsoever, except with the written permission of Insmmed Incorporated.*

### 7.2.2.2 Assessment

Significant findings at Baseline (Day 1) and any changes from Baseline (Day 1) prior to first dose of LAI or multi-drug regimen at Day 1 must be recorded in the Medical History/Current Medical Conditions pages of the eCRF. Significant findings made after the Baseline (Day 1) visit that meet the definition of an AE must be recorded on the Adverse Event page of the eCRF.

### 7.2.3 Vital Signs

#### 7.2.3.1 Methodology

Five-minute sitting blood pressure, pulse rate, body temperature, respiratory rate, and oxygen saturation will be recorded in the eCRF at every scheduled visit except at Months 1, 3, 5, 10, 14, at 28 days and 6 months off-treatment.

At visits when the 6MWT is administered (at Baseline [Day 1], at Months 4, 6, and 8 and at EOT and 3 months off-treatment) vital signs will be measured before and after subjects walk a prescribed course as far as they can in 6 minutes.

#### 7.2.3.2 Assessment

Significant findings observed at any time after the first dose of LAI or multi-drug regimen that meet the definition of an AE must be recorded on the Adverse Event page of the eCRF.

### 7.2.4 Pulmonary Function Tests

Pulmonary function tests (FEV1[L], FEF(25-75%), FVC) will be performed at sites with access to spirometers and trained personnel to perform spirometry at Baseline (Day 1), Month 6 for all subjects and at the 6-months off-treatment visit only for subjects completing LAI treatment. All subjects undergoing PFTs should be optimally treated for their underlying lung disease before these assessments are performed. Additionally, for subjects randomized to the LAI plus multi-drug regimen arm they will be performed prior to the administration of LAI. If necessary, per the discretion of the Investigator, subjects randomized to LAI may have pre- and post-dose PFTs performed to determine the degree of sub-clinical bronchospasm and airway obstruction so

Protocol Amendment #3 version: 22 February 2016

*This protocol is solely for the purpose of communicating information about the investigational drug between Insmmed Incorporated and study personnel. Information is not to be reproduced, abstracted or used for sharing of information for any other purpose, whatsoever, except with the written permission of Insmmed Incorporated.*

appropriate management can be commenced prior to LAI dosing. . More information will be provided in a separate manual provided by the Sponsor.

#### **7.2.4.1 Assessment**

The pulmonary function parameters of forced expiratory volume in 1 second (FEV1[L]), forced expiratory flow rate during mid portion of expiration (FEF(25-75%)) and forced vital capacity (FVC) based on local assessments will be recorded on the specific page within the eCRF. Any clinically significant findings observed must be recorded on the Adverse Event page of the eCRF.

#### **7.2.5 12-lead Electrocardiogram**

##### **7.2.5.1 Methodology**

An ECG will be recorded at Screening and EOT.

##### **7.2.5.2 Assessment**

The Screening ECG will be considered as Baseline. The date and interpretation (Normal; Abnormal – not clinically significant; Abnormal – clinically significant) must be recorded within the ECG page of the eCRF. Any abnormal – clinically significant findings at Baseline (Day 1) and any changes from Baseline (Day 1) prior to first dose of LAI or multi-drug regimen at Day 1 must be recorded in the Medical History/Current Medical Conditions pages of the eCRF. Any abnormal – clinically significant findings made after the Baseline (Day 1) visit that meet the definition of an AE must be recorded on the Adverse Event page of the eCRF.

#### **7.2.6 Adverse Events**

##### **7.2.6.1 Methodology**

AEs will be identified at every contact with a subject throughout the study period beginning with Day 1 and after first dose of LAI or multi-drug regimen by direct observation, from assessments of safety parameters, and by asking open-ended, non-leading questions such as “How have you felt since your last visit?” See [Section 8](#) for definitions and a fuller description of the assessment

Protocol Amendment #3 version: 22 February 2016

*This protocol is solely for the purpose of communicating information about the investigational drug between Insmmed Incorporated and study personnel. Information is not to be reproduced, abstracted or used for sharing of information for any other purpose, whatsoever, except with the written permission of Insmmed Incorporated.*

and reporting requirements of AEs. Any AE that is observed prior to first dose of LAI or multi-drug regimen will be classified as medical history.

### 7.2.6.2 Assessment

All AEs will be recorded on the Adverse Event page of the eCRF. Attempts will be made to determine the start and stop dates of the event, the intensity, causality, treatment, and outcome of the event. Any AE that is observed prior to first dose of LAI or multi-drug regimen must be recorded on the Medical History page of the eCRF.

